10.2 Determination of Sample Size

Since this is an extension study, sample size is determined by the number of patients who completed HGT-SAN-055 (maximum of 12 patients) and elected to continue treatment with HGT-1410 in this study. Hence no statistical estimation of the sample size was performed.

10.3 Analysis Populations

The primary analysis population consists of all eligible patients from HGT-SAN-055 who have agreed to participate in the extension study. This population will be used to perform both safety and efficacy analyses. The collection of detailed data pertaining to the SOPH-A-PORT mini S will permit device-related analyses to be conducted in the subset of patients in the primary analysis population who had the SOPH-A-PORT Mini S implant procedure performed.

10.4 Demographics and Baseline Characteristics

Patient disposition for those enrolled will be presented in a summary table using number and percentage of patients enrolled, completed or discontinued/withdrew. The reasons for discontinuation/withdrawal will also be presented.

Demographic and baseline characteristics (eg, age, race, ethnicity, medical history, and surgical history) will be reported in summary tables.

10.5 Statistical Analysis of Pharmacokinetic Variables

Not applicable.

10.6 Efficacy, Safety, and Pharmacodynamic Evaluations

10.6.1 Primary Analyses

10.6.1.1 Safety Analysis

In general, safety assessments will be based on all assessments post-baseline. The assessment of safety will be based primarily on the frequency of AEs, and on the frequency of clinically notable abnormal vital sign and laboratory values. Changes from baseline will be calculated by subtracting the baseline value from the post-baseline value.

All enrolled patients who had an IDDD surgical procedure and/or received administration of HGT-1410 will be included in the safety analysis.

Adverse events will be recorded throughout the study and at early termination. Adverse events and medical conditions will be coded using the Medical Dictionary for Regulatory Activities (MedDRA).

Adverse events will be summarized by presenting, for each dose group, the number and percentage of patients having any AE, having an AE in system organ class, and having each individual AE. In addition, those events which resulted in death or were otherwise classified as serious will be presented in a separate listing. The incidence of treatment-emergent adverse events, defined as all AEs from the time of the surgery for IDDD implantation to the last follow up contact, ie, 30 days after the last HGT-1410 administration, (new or worsened from baseline) will be summarized by system organ class, severity, type of adverse event and relationship to trial medication/procedure.

Treatment-emergent AEs deemed related to HGT-1410 administration will be summarized separately.

IDDD, and procedure-related AEs will be summarized within system organ class by preferred term. IDDD and procedure-related AEs will be tabulated by severity (mild, moderate, severe) and degree of relatedness. Separate tabulations will be provided for adverse events related to the IDDD, device surgical procedure (including post-implant infections) and IT administration process. These summaries will be presented by device and overall, as appropriate.

Descriptive summaries of clinical laboratory evaluations (hematology, serum chemistry, urinalysis and CSF) results will be presented in summary tables by evaluation visit. Changes from baseline will be summarized for each post-baseline visit. Each laboratory result will be categorized as a patient having had (1) an Abnormal and Clinically Significant (CS) value at any time, (2) no CS values at any time but had at least one Abnormal and not CS (NCS) value, and (3) no CS or NCS values at any time; the number and percentage in each category will be presented. For any patient who experiences a CS laboratory result at any time that was not CS at

baseline (or the most recent non-missing value prior to the start of the treatment), their entire profile for that particular laboratory parameter will be presented as a listing.

The observed values and changes from baseline for vital sign data will be summarized for each dose group. Shift tables may be presented, utilizing reference ranges. Patients with notably abnormal values will be identified and listed separately along with their values.

The observed values and changes from baseline for ECG data will be summarized for each dose group. Patients with any clinically significant findings and/or conduction abnormalities will be listed separately along with their values.

Anti-rhHNS antibody formation will be monitored throughout the study. Results will be presented in summary tables by number and percentage of positive and negative specimens by evaluation visit, and number and percentage of positive and negative specimens overall. The effect of antibodies on other safety parameters will be assessed by presenting summary tables by antibody status.

For those patients who fail to complete the study, the reason for discontinuation will be listed by patient and dose group.

Listings of all study safety data will be presented.

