2 STUDY OBJECTIVES

2.1 Primary Objective

The primary objective of this study is:

- To collect long-term safety and tolerability data in patients with Sanfilippo Syndrome Type A (MPS IIIA) who received HGT-1410 via a surgically implanted IDDD in study HGT-SAN-055 and elect to continue therapy in study HGT-SAN-067.

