3 STUDY ENDPOINTS

3.1 Primary Endpoint

The primary endpoints of this study are related to the long-term safety of intrathecal HGT-1410 administration. The safety endpoints are:

[figure not shown]
- adverse events (type and severity)
- changes in clinical laboratory testing (serum chemistry including liver function tests, hematology, and urinalysis)
- electrocardiograms (ECG)
- cerebrospinal fluid (CSF) chemistries (including cell counts and inflammatory markers)
- anti-rhHNS antibodies (in CSF and serum).

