4.3 Study Duration and Dates

The study duration will be 4 years.

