6.3 Selection and Timing of Dose for Each Patient

Patients will check into the study center 1 day prior to IT HGT-1410 dosing for safety assessments, designated Day 1, on each HGT-1410 treatment week, and if no safety concerns exist, will receive IT administration of HGT-1410 on Day 2 (± 2 days). However, if feasible and there are no safety concerns in the opinion of the Investigator, the Day 1 and Day 2 assessments and dosing may be combined and performed on Day 2; if this is done the results will be recorded as Day 2. Patients will remain in the study center for at least 4 hours following dosing with HGT-1410 and will be discharged from the unit when deemed clinically stable by the Investigator.

The IT injections are to be administered every 28 days (± 7 days). If a patient's IDDD becomes nonfunctional, it may be revised (partial or complete) (a maximum of twice in a 6 month period) so that the patient can remain on study (see Section 7.12 for details). In the event of a non-functional IDDD, HGT-1410 may be administered by LP, for up to 5 successive months (see Section 6.3.3).

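### Adverse events over about 52 doses are summarised only as patients ever affected; add event counts and exposure-based rates by time on treatment and by dose at onset

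*Protocol*

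**What the plan says.** The primary objective (Protocol section 2.1) is "To collect long-term safety and tolerability data in patients with Sanfilippo Syndrome Type A", and section 3.1 lists adverse events, by type and severity, first among the primary endpoints. On timing, section 6.3 says "The IT injections are to be administered every 28 days" and section 4.3 says "The study duration will be 4 years".

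Section 10.6.1.1 then sets the analysis. It says "The assessment of safety will be based primarily on the frequency of AEs", together with notable vital sign and laboratory abnormalities. Frequency is not defined as events or as patients, but the summary that follows is per patient and per dose group: the "number and percentage of patients having any AE, having an AE in system organ class, and having each individual AE". Treatment-emergent events are "defined as all AEs from the time of the surgery for IDDD implantation to the last follow up contact", and their incidence is broken down by system organ class, severity, type and relationship. The adverse event paragraphs name no event count, no exposure denominator and no time interval.

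Other parts of section 10.6 are fuller. Laboratory results and antibodies are summarised by visit. Section 10.6.2.1 gives device failures and malfunctions a count, a rate with a 95% confidence interval, and a time to first event with censoring.

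**The concern.** In a study of monthly dosing over four years, many adverse events recur. A patient-ever percentage gives one headache the same weight as forty, and an event at the first extension dose the same weight as one in year 4. It also gives a patient who leaves in the first year the same place in the denominator as one who completes, and section 7.27 says leavers are not replaced.

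What is at stake is how much the main adverse event tables can tell a reader about long-term tolerability: whether events become more or less frequent with time, and whether a group with many recurrences differs from one with few. The dose-group label adds a further difficulty. Group 1 moves from 10 mg to 45 mg (sections 6.2 and 6.4), so one cumulative row for that group mixes two doses.

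**Working it through.** The protocol states no adverse event rate, sample-size calculation or power, so there is no figure of the plan's own to reproduce.

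**Inputs from the protocol**
- Dosing interval 28 days (section 6.3).
- 48 months in the extension (section 4.3; Appendix 1 adds 6 months of the parent study, 54 in all).
- At most 12 patients (section 5.1) in three dose groups.

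**Assumptions**
- Per-dose risk p of a given event, over a range.
- Independent dosing intervals.
- 4 patients per group (12/3; the split is not given).

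**Step 1: exposure.** Doses = months × 30.4375 / 28. For 48 months: 48 × 30.4375 / 28 = 52.2, about 52. For 54 months: 58.7, about 59.

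**Step 2: chance that a patient is ever affected,** 1 − (1 − p)^52:

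| p per dose | ever affected | expected events per patient (52p) |
|---|---|---|
| 0.5% | 23% | 0.26 |
| 1% | 41% | 0.52 |
| 2% | 65% | 1.04 |
| 5% | 93% | 2.6 |
| 10% | 99.6% | 5.2 |
| 20% | 100% | 10.4 |

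The expected number of events doubles when the risk doubles. The percentage does so less and less: 41% to 65% for 1% against 2%, but 93% to 99.6% for 5% against 10%.

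**Step 3: two groups of 4, one with twice the risk of the other.** The chance that both show 4 of 4 affected is P1^4 × P2^4:
- 1% against 2%: 0.5%
- 5% against 10%: 0.931^4 × 0.996^4, about 74%
- 10% against 20%: 98%

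**Step 4: what an event rate adds.** Four patients for 4 years give 16 patient-years. If all four are affected, the percentage is 100% (exact 95% CI 40% to 100%) whatever the number of events. With 32 events the rate is 32/16 = 2.0 per patient-year (exact Poisson 95% CI 1.37 to 2.82). With 64 it is 64/16 = 4.0 (3.08 to 5.11). These intervals ignore clustering within patient, so honest ones would be wider.

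**Step 5: unequal follow-up.** Take p = 2% and a patient who leaves around Month 15, that is 9 months into the extension: 9 × 30.4375 / 28 = 9.8, about 10 doses. The chance of being counted is 1 − 0.98^10 = 18%, against 1 − 0.98^52 = 65% for a completer. In a group of 4 with two such leavers, the expected percentage is (2 × 65.0 + 2 × 18.3)/4 = 41.7%. That is close to the 40.7% expected from four completers at half the risk (1 − 0.99^52).

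**The case against.** The strongest reply is that this is table-shell detail. Section 10.6.3.2 ends by leaving planned analyses and presentations to the SAP, which is not at hand and may well contain event counts and exposure-adjusted rates. Section 10.6.1.1 does not say that patient percentages are the only summary, and patient-level incidence is standard. This stands in part: the absence of rates from the protocol does not show that they are absent from the SAP, and the point is an improvement, not an error. But the protocol is not silent here. It chose the adverse event statistic, and for devices it wrote in counts, a rate and time to first event.

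The listings of all safety data, together with recorded onset dates, also let a reader recover recurrence and timing for at most 12 patients. That is true, but it is a recount by hand and not a summary of a primary endpoint.

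A reader might go further than the document allows in four ways.
- **All adverse event tables will read near 100%.** No rates are given, and at an assumed 2% per dose or less they will not.
- **Differences in long-term safety cannot be shown at all.** The by-visit laboratory and antibody summaries, the device analyses and the listings say otherwise.
- **Laboratory data share the fault**, because "Each laboratory result will be categorized as a patient having had (1) an Abnormal and Clinically Significant (CS) value at any time". That category is for clinically significant values, so it does not fill up with chance excursions outside reference limits. By-visit summaries and full-profile listings for new clinically significant results stand beside it.
- **The summary costs statistical power between doses.** Section 10.1 plans no hypothesis tests, and with about 4 patients per group any dose comparison is weak.

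Nor is the endpoint itself defined as ever or never affected; the reduction lies in the planned summary.

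**Conclusion.** The point holds as a worthwhile, inexpensive improvement to section 10.6.1.1. The adverse event summary written there discards recurrence, timing and length of follow-up, which matter for a long-term safety objective over about 52 doses.

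Its size depends on event rates that the protocol does not give. Under the assumptions of independent intervals and 4 patients per group, the any-AE row and events with a risk of about 5% or more per dose will be close to 100% in every group, and a doubling of risk will usually leave no trace (both groups at 4 of 4 in 74% to 98% of cases). Less frequent events do not saturate, but their percentages are pulled down by early leavers: at 2% per dose, 18% after 10 doses against 65% after 52. How far this bites depends on how many patients leave early, which is also unknown.

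**What to change.** Keep the patient percentages. In section 10.6.1.1, for the adverse event tables (overall, system organ class, preferred term, and drug-related events), add:
- the number of events;
- the event rate per patient-year, or per injection, with a 95% confidence interval that allows for clustering within patient where there are enough events, and the count and rate alone where there are not;
- the same by time-on-treatment interval, for example Months 6–12, 12–24, 24–36 and 36–54 on the protocol's month scale;
- the same by dose received at onset, with patient-time divided at the change from 10 mg to 45 mg, so that numerator and denominator refer to the same dose.

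If the SAP already specifies these, a cross-reference from section 10.6.1.1 is enough.

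No new data and no added burden on patients are needed: section 7.23.5.2 has onset and resolution dates recorded for each event, and section 6.3.2 has injection date and planned dose recorded on the eCRF. The cost is slightly longer tables and, with at most 12 patients, wide intervals that should be read descriptively.

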3.3 SOPH-A-PORT Mini S Assessments

4 INVESTIGATIONAL PLAN

4.1 Overall Study Design and Plan

Study HGT-SAN-067, is an open-label, long term, multicenter, extension of Study HGT-SAN-055. This study is designed to evaluate the long-term safety, clinical activity, and biomarker outcomes of IT administration of 3 dose levels (10 mg, 45 mg, and 90 mg once per month [Q4W]) of HGT-1410 via an IDDD in patients with MPS IIIA who successfully completed HGT-SAN-055 (including the EOS assessments) and elect to continue to receive uninterrupted HGT-1410 treatment. Patients will initially continue in the same treatment group they were assigned to in the HGT-SAN-055 study:

- Group 1: HGT-1410 administered by IT injection 10 mg once per month (Q4W)
- Group 2: HGT-1410 administered by IT injection 45 mg once per month (Q4W)
- Group 3: HGT-1410 administered by IT injection 90 mg once per month (Q4W)

Patients assigned to Group 1 will initially receive 10 mg monthly but will have their dose increased to 45 mg monthly (Q4W) at the first administration of HGT-1410 following full approval of protocol Amendment 4.

In order to maintain a nomenclature system based on study chronology across the original HGT-SAN-055 study and this extension study, the Baseline Visit for this extension study will be considered to be the day the patient received their first IT dose of HGT-1410 in Study HGT-SAN-055. The HGT-SAN-055 EOS assessment information will provide the screening/start of study information for patients who continue into the HGT-SAN-067 extension study. Note: HGT-SAN-055 EOS data must be recorded in the context of the HGT-SAN-055 trial, and a copy of those data can be used for HGT-SAN-067 screening. Once eligibility is confirmed, informed consent (and assent, if applicable), provided by the patient's parent(s)/legally authorized representative(s), must be obtained prior to performing any HGT-SAN-067 study-related procedures. Informed consent may be obtained anytime from Week 20 in HGT-SAN-055. This would allow a patient to have a nonfunctional IDDD replaced or revised prior to the first HGT-1410 dose in HGT-SAN-067.

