Patients will be evaluated for safety throughout the study. Adverse events that occur in HGT-SAN-055 and are ongoing at enrollment in HGT-SAN-067 will be captured as ongoing in the HGT-SAN-055 study and also be reported as a concurrent condition in the HGT-SAN-067 eCRFs. Specific safety stopping criteria will be applied and will be based on the types and severity of AEs reported while on-study. These data will be reviewed to inform the decision to discontinue a patient, a dose group, or the study as a whole.

All patients will have an EOS visit 30 (\pm 7) days following their last administration of HGT-1410 (ie, Month 55). The EOS procedures will include standard clinical laboratory tests (serum chemistry, hematology, and urinalysis) in CSF and blood, protocol specific laboratory testing (eg, anti-rhHNS antibody testing), neurodevelopmental testing, ABR, child health questionnaires, MRI and X-ray examination of the device. Use of concomitant medications, therapies, and procedures will be recorded and AEs will be monitored.

All patients will be contacted by telephone or will have a visit for a Final Safety Follow-up, conducted at 30 (\pm 7) days after the EOS visit (ie, Month 56) to collect updated information on AEs and concomitant medications, therapies, and procedures.

It is anticipated that the IDDD will be used to obtain CSF samples and to administer HGT-1410. However, if a patient's PORT-A-CATH IDDD appears nonfunctional or if its use is precluded on a scheduled day of dosing, site personnel will refer to the PORT-A-CATH Instructions for Use (IFU), which describes the investigation and management of IDDD-related issues with this device. This will include possible partial revision or complete replacement of the PORT-A-CATH IDDD with a SOPH-A-PORT IDDD. For malfunctions involving the SOPH-A-PORT Mini S, site personnel will refer to the SOPH-A-PORT IFU. For either IDDD, a maximum of 2 partial revisions and/or complete replacements are permitted in any 6 month period (including participation in study HGT-SAN-055). If a revision or replacement of the IDDD cannot be scheduled in time to avoid a delay of the next scheduled dose of HGT-1410, or if the patient experiences more than 2 IDDD malfunctions in a 6 month period, HGT-1410 will be

administered via lumbar puncture (LP). Drug may be administered via LP for a maximum of 5 successive monthly doses, after which, IDDD re-implantation or revision must occur.

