7.23 Adverse Events

7.23.1 Definitions of Adverse Events and Serious Adverse Events

7.23.1.1 Adverse Event

An AE is any noxious, pathologic, or unintended change in anatomical, physiologic, or metabolic function as indicated by physical signs, symptoms, or laboratory changes occurring in any phase of a clinical study, whether or not considered study drug-related. This includes an exacerbation of a pre-existing condition. Once the informed consent is signed and dated, any adverse event prior to the start of study drug must be reported.

AEs include:

- Worsening (change in nature, severity, or frequency) of conditions present at the onset of the study
- Intercurrent illnesses
- Drug interactions
- Events related to or possibly related to concomitant medications
- Abnormal laboratory values (this includes significant shifts from baseline within the range of normal that the Investigator considers to be clinically important)
- Clinically significant abnormalities in physical examination, vital signs, and weight

Throughout the study, the Investigator must record all AEs on the AE eCRF, regardless of the severity or relationship to study drug. The Investigator should treat patients with AEs appropriately and observe them at suitable intervals until the events stabilize or resolve. AEs may be discovered through observation or examination of the patient, questioning of the patient, complaint by the patient, or by abnormal clinical laboratory values.

In addition, AEs may also include laboratory values that become significantly out of range. In the event of an out-of-range value, the laboratory test should be repeated until it returns to normal or can be explained and the patient's safety is not at risk.

All AEs should be recorded with causality assessment.

The information presented below is intended to provide issues to consider for AEs associated with intrathecal injections of HGT-1410. In general, these AEs can be classified as follows:

- Adverse events due to systemic exposure to HGT-1410 caused by the drug diffusion from the CSF to the peripheral circulation;
- Adverse events related to the direct delivery of HGT-1410 to the intrathecal CSF space and meninges, and subsequent diffusion into brain parenchyma, via an intrathecal route
- IDDD-related AEs

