8.2.1.2 Day 2 (± 2 days) Assessments and Administration of HGT-1410

Patients may be discharged from the clinical site 4 hours after dosing, if deemed stable by the Investigator.

- Physical examination
- ECG (performed following IT study drug injection)
- Vital signs
- CSF sample collection (obtained prior to IT study drug injection)
- HGT-1410 IT injection (Day 2 ± 2 days)
- Neurological examination
- Concomitant medications, therapies, and procedures
- AE assessments

The neurological exam should not occur sooner than 4 hours after study drug administration or before the patient has fully recovered from any anesthesia administered for the dosing, whichever occurs later.

8.3 End of Study/Early Termination Procedures: Month 55

Patients who complete the study or who discontinue prior to the end of the study, will have EOS assessments performed 30 (± 7 days) after their last dose of HGT-1410.

Patients who discontinue or are withdrawn prior to study completion will be asked to participate in the EOS procedures at the time of discontinuation. Participation in these EOS procedures will be strongly encouraged, but is voluntary for those patients electing to discontinue from the study. Note: Patients will have the IDDD removed when they discontinue from the study, unless the patient is continuing to receive treatment through another mechanism (eg, expanded access, commercially available).

- Physical examination
- Height and weight
- Head circumference
- Visual and hearing assessment
- ECG
- Vital signs
- Hematology
- Serum chemistries
- Urinalysis
- Urine heparan sulfate and heparan sulfate derivatives
- Plasma and serum heparan sulfate and heparan sulfate derivatives
- Anti-rhHNS antibody testing
- ABR (unless performed at Month 54)
- MRI of the head (unless performed at Month 54)
- CSF sample collection (unless performed at Month 54)
- Neurological examination
- Full neurodevelopmental testing, including VABS-II
- Children's Sleep Habits Rating Scale
- Child health questionnaire-50
- Child health questionnaire-87
- Infant toddler QoL Questionnaire
- Concomitant medications, therapies, and procedures
- AE assessments
- X-ray of device, if the patient is to continue to receive intrathecal HGT-1410 beyond the end of the study

All patients who discontinue the study early will have their IDDD removed.

Patients who withdraw or discontinue after having received fewer than 3 IT injections will not need to complete the EOS visit.

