Patients who withdraw or discontinue from the study after having received 3 or more IT injections, will be asked to complete the EOS visit and undergo all the scheduled assessments.

8.4 Safety Follow-up (by Telephone or Visit) Month 56

Patients who complete the study or withdraw early will have a safety follow-up telephone call or visit 30 Days (± 7 days) after the last study visit. This will assess:

- Concomitant medications, therapies, and procedures
- AE assessments

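### The treatment-emergent AE window equates the last follow-up contact with day 30 after the last dose, but the schedule puts that contact at about day 60

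*Protocol*

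**What the plan says.** Section 10.6.1.1 (Amendment 5, with the same wording in Amendment 4) runs the treatment-emergent window "from the time of the surgery for IDDD implantation to the last follow up contact, ie, 30 days after the last HGT-1410 administration". Events must also be new or worsened from baseline. Summaries by organ class, severity, event type and relationship rest on this definition, as does a separate summary of drug-related treatment-emergent events.

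The visit schedule is stated elsewhere and is consistent:

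- Section 8.3: patients who complete or discontinue "will have EOS assessments performed 30 (± 7 days) after their last dose of HGT-1410". Section 4.1 and note f to the Appendix 1 schedule agree; this is Month 55.
- Section 8.4: the safety follow-up, which assesses adverse events, is "30 Days (± 7 days) after the last study visit".
- Section 4.1: the final safety follow-up is 30 (±7) "days after the EOS visit (ie, Month 56) to collect updated information on AEs and concomitant medications, therapies, and procedures". The synopsis and note j to the schedule give the same interval.

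On the front end, Section 2.1 places the device implantation in HGT-SAN-055, and Section 4.1 sets baseline at the first dose in that study. Parent-study events still ongoing at enrollment "will be captured as ongoing in the HGT-SAN-055 study and also be reported as a concurrent condition in the HGT-SAN-067 eCRFs". Section 7.23.1.1 adds: "Once the informed consent is signed and dated, any adverse event prior to the start of study drug must be reported". Section 4.1 allows early consent: "Informed consent may be obtained anytime from Week 20 in HGT-SAN-055".

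**The concern.** The definition offers two end points, about a month apart, as if they were one. A programmer must choose. Following the words gives the Month 56 contact; following the number gives roughly the EOS visit.

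Adverse events are the first-listed primary endpoint (Section 3.1), and Section 10.6.1.1 rests the safety assessment mainly on their frequency. Under the day-30 choice, events elicited at the Month 56 contact with onset after day 30 drop out of the treatment-emergent tables, although that contact exists to collect them. Section 4.1 has the device removed as part of the EOS procedures when a patient discontinues or the sponsor stops the study. For those patients the recovery period after removal is largely what would be cut off, and Section 7.23.1.3 names explant and removal among its surgical-procedure events.

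With at most 12 patients (Section 10.2), a single reclassified patient can move an overall incidence by 1/12, about 8 percentage points, if that patient has no earlier event of the same kind.

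**Working it through.** **Inputs**, in days:

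- Limit stated in Section 10.6.1.1: day 30 after the last dose, with no tolerance.
- E, last dose to EOS: 30 ± 7, so 23 to 37 (Sections 4.1 and 8.3; schedule note f).
- F, EOS to final safety contact: 30 ± 7, so 23 to 37 (synopsis; Sections 4.1 and 8.4; schedule note j).

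**Formula.** Last contact L = E + F, counted from the last dose.

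**The plan's own figure.** L = 30 results nominally only if F is set to 0, so that EOS is treated as the last contact, or if there is no EOS visit and L = F.

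| Case | E | F | L | L − 30 | (L − 30)/L |
|---|---|---|---|---|---|
| Earliest | 23 | 23 | 46 | 16 | 35% |
| Nominal | 30 | 30 | 60 | 30 | 50% |
| Latest | 37 | 37 | 74 | 44 | 59% |

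The earliest possible contact, day 46, is already past day 30. EOS itself can fall on days 31 to 37, also past the limit.

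**Patients without EOS.** Section 8.3 excuses patients with fewer than 3 injections from EOS. If their last visit was a dosing visit, the last contact is day 23 to 37, and the 30-day figure roughly fits. A discontinuing patient who declines the voluntary EOS visit would be in the same position.

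**Device removal.** Removal at EOS falls on day 23, 30 or 37. A day-30 limit then covers 30 − E = 7, 0 or −7 days after removal; a negative value means the removal itself lies outside the window. Completers differ: note q to the schedule puts their removal at the Month 54 visit. That is the visit of the last dose, since EOS at Month 55 is 30 days after it. About 30 days after removal are therefore covered.

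**Scale.** Against this study's whole span, Month 6 to Month 56, the disputed period is about 1 month in 50, or 2%.

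**Front end, side by side.** The definition says which event opens the window but not which surgery. The initial one was in the parent study and precedes the baseline used for judging new or worsened events. A later replacement under Section 6.1.2 is also an implantation, but not every patient need have one. The parent-study surgery is therefore the only reading sure to give every patient a start date. Whether parent-study adverse events are then brought into the analysis is not stated.

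**The case against.** The strongest reply is that the operative words are the last follow-up contact and the 30-day gloss is a slip, so nothing need be lost. That stands to this extent: the defect is a contradiction, and exclusion follows only if the number is applied.

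Nor would the events vanish. Section 10.6.1.1 also plans counts of patients with any adverse event, a listing of deaths and serious events, and separate device, surgical-procedure and administration tabulations, none worded as limited to treatment-emergent events. Listings of all safety data are promised too. What is lost is the treatment-emergent label and the tables built on it. The post-removal example is confined mainly to early discontinuation or a sponsor stop, and patients continuing treatment by another mechanism keep the device (Section 7.13.4).

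A reader might infer that the window is equally wrong at its start, because it opens in the parent study and parent-study events enter here only as concurrent conditions. The documents do not support that. A parent-study start fits the protocol's baseline, the first HGT-SAN-055 dose, provided the two studies' adverse event data are combined, and nothing rules that out. Ongoing events stay recorded in HGT-SAN-055 and are reported here in addition. Events after early consent are reported in this study whether or not they later resolve. What remains is an unspecified start, which calls for clarification.

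Leaving the matter to the analysis plan does not answer the end-point problem. The protocol fixed a day count that its own schedule contradicts.

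**Conclusion.** The end of the treatment-emergent window is misstated. For a patient with an EOS visit, the last adverse-event contact is nominally day 60 after the last dose (46 to 74), not day 30. Applying day 30 leaves 30 days of scheduled collection (16 to 44) outside the window: half of nominal post-dose follow-up, but only about 2% of the time in this study. Both proportions should be kept in view.

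The figures assume EOS is timed from the last dose as stated. Section 8.3 also asks discontinuing patients to undergo the EOS procedures at discontinuation, and their last contact would shift accordingly. The number of events affected cannot be estimated from the protocol.

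The point deserves correction because the rule governs the first-listed primary endpoint and the correction is nearly free. It does not show that safety events go unreported or that the parent-study start is an error.

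**What to change.** In Section 10.6.1.1, delete the phrase equating the last contact with 30 days after the last dose. End the window at the Month 56 safety follow-up contact, 30 (±7) days after EOS, or at the last contact for patients without an EOS visit.

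As a secondary clarification in the same section, name the implantation that opens the window and say how events between that surgery and the first HGT-SAN-055 dose are judged new or worsened, since they precede baseline. State whether HGT-SAN-055 adverse events are integrated; if so, count once any event reported in both studies after early consent.

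The end-point correction costs one clause and needs no new data, visits or case report form changes. If the parent study is integrated, the added work is combining two sets of adverse event records and removing duplicates. Neither change requires altering the analysis population or how ongoing parent-study events are recorded.
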